#### Adequacy of protection against risks

Phlebotomy: Blood draws will be performed by trained personnel with expertise in pediatric phlebotomy and follow hospital standards for phlebotomy. All blood obtained during this trial will be collected at the same time as standard of care labs to minimize extra risk of an additional blood draw.

Urine samples: Obtaining participant urine samples will follow hospital standards for urine collection and occur in a private setting

History and physical exam: Participants will undergo a monthly history and physical by an experienced sickle cell practitioner.

Participant confidentiality: To protect confidentiality, every participant will be assigned a study identification number that is unique. The link between participant name and study ID will be kept on a locked, password protected computer that is separate from the locked, password

protected computer used to enter participant information. All study forms will be entered using the study ID number. Data will be retrieved using the study ID number.

## Data Safety and Monitoring Board

We will identify investigators (at least 4 members to include a pediatric hypertension expert, sickle cell expert, patient representative, and biostatistician) to participate in an independent DSMB to monitor study safety and minimize research associated risk. Incidence of adverse events during the 6 month period will be analyzed during all mentoring meetings and independently by the DSMB. The percentage and 95% confidence intervals for serious adverse events and adverse events will be recorded and sent to DSMB every 3 months. The DSMB will evaluate excessive SAEs overall or in any one group and consider either: 1) reducing the dose of losartan or 2) closing the study and offering an alternative hypertensive medication. Patients will be withdrawn from the trial if they experience angioedema, recurrent symptomatic hypotension despite dose reduction, hyperkalemia, or recurrent symptomatic hypoglycemia.

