## 2.2 Randomized Feasibility Trial-

A randomized feasibility trial of losartan for the correction of abnormal nocturnal blood pressure dipping in adolescent patients with HbSS or SB0 thalassemia 11-22 years of age who have documented hypertensive blood pressure in clinic will be conducted. Participants will be randomized to losartan at doses to maintain clinic BP either <95th percentile (standard dosing strategy) or <75th percentile (intensive dosing strategy). The study will be analyzed using intention to treat for outcomes which will begin immediately after randomization to losartan. Participants will be followed monthly as standard of care with additional research procedures of performing ambulatory blood pressure monitoring at baseline, 3 months, and 6 months and urine/blood biomarkers of kidney injury at baseline, 3 months and 6 months. We propose to identify 60 eligible participants of which 40 will participate in the randomized feasibility trial. The parents/legal guardians of these children will have a one hour educational session on hypertension and kidney disease in sickle cell disease. The parents/legal guardians will be offered the opportunity to discuss hypertension and kidney disease with a Pediatric Nephrologist prior to participation in the trial.

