## 7. Safety Reporting and Adverse Events

All patients will have standard of care monthly clinic visits while on losartan. Side effects and adverse events will be recorded by study coordinator at each clinic visit. Participants will have monthly complete metabolic profiles for monitoring of potassium, liver function tests. Participants will be asked about symptoms of hypotension.

**Hyperkalemia:** Participants will have potassium monitored monthly. Potassium > 6 mEq/L will be repeated and if abnormal, the dose of losartan will be decreased. If participants are still >95th percentile blood pressure when hyperkalemia, a diuretic will be added as standard of care.

**Liver function tests:** Participants baseline AST and ALT will be recorded and compared to monthly AST and ALT levels. If AST/ALT is greater than three times the upper limit of normal, losartan will be stopped

**Symptomatic hypotension:** Participants will be asked about symptoms of hypotension prior to enrollment and at each visit including feeling lightheaded or dizzy. Participants will be asked to call the study PI to notify them of symptoms and take a blood pressure at home.

**Allergic reaction:** Participants will be asked to call the study PI if they develop swelling of the face, lips, throat, and/or tongue. Participants will be asked to describe any new rashes.

**Musculoskeletal:** Participants will be asked to describe any muscle pain, muscle tenderness, or dark urine.

Additional AEs will be documented based on participant interview and voluntary disclosure of additional toxicities. AEs will be scored using the Common Toxicity Criteria for Adverse Events 4.0.

[http://evs.nci.nih.gov/ftp1/CTCAE/CTCAE\\_4.03\\_2010-06-14\\_QuickReference\\_5x7.pdf](http://evs.nci.nih.gov/ftp1/CTCAE/CTCAE_4.03_2010-06-14_QuickReference_5x7.pdf)

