### 9.2. Analysis:

Objective 1: To demonstrate in a feasibility trial the optimal dose of losartan and effect size necessary to conduct a trial of losartan in participants with abnormal nocturnal dipping.

Objective 2: Demonstrate the Acceptability of and Barriers to Enrollment into a Feasibility Trial of Losartan.

Objective 3: Demonstrate and Promote Adherence to Study Medication during Feasibility Trial

Objective 4: Demonstrate Adherence to Study Procedures and Retention in the Clinical Trial.

Analysis for Objective 1: The feasibility trial will evaluate two dosing strategies of losartan. The DSMB will be instrumental in evaluating safety of losartan during the course of the trial. At the end of the trial, the two dosing strategies for losartan will be directly compared using student's t-test. The effect size necessary to conduct a definitive trial will be obtained through identifying the acceptance rate (objective 2), adherence/dropout rate (objective 3 and 4). The correction of abnormal nocturnal dipping will be evaluated using

continuous data. To properly power a definitive trial, this feasibility trial will document the standard deviation/variability in BP among participants, the estimated difference in nocturnal blood pressure at baseline and exit.

Analysis for Objective 2: The acceptance rate will be defined by the percent of participants enrolled divided by the number of patients approached for enrollment. The acceptability of the trial will be defined by evaluating barriers or facilitators to enrolling in this feasibility trial. Dichotomous dependent variables will be created for participants that enroll or do not enroll in the study. Independent variables will reflect (ordinal) responses provided during the survey. Bivariate relationships will be tested using chi-square or Fischer's exact tests and/or logistic regression. The mentorship team will review the identified barriers and facilitators to enrollment and develop strategies to enhance enrollment in future BP trials. For example, if mistrust is a barrier, a future strategy enrollment may include peer-delivered video testimonials.

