Analysis for Objective 3. [name] will mentor [name] in the analysis of medication adherence during a clinical trial. Specifically, the adherence rates will be reviewed for each individual participant and for all participants over time to determine feasibility of losartan adherence over the six month trial. In addition, the effect of adherence interventions (calendar, phone calls) on losartan will be reviewed as well as participant reasons stated for good/poor adherence. The mentoring team will review adherence reports and work to develop an intervention plan for enhanced adherence during the planned definitive trial.

Analysis for Objective 4: To effectively design a multicenter trial, it is vital to understand the rate and barriers to trial retention and feasibility of repeated ABPM prior to conducting a SCD hypertension trial. The retention rate will be recorded and re-evaluated against the initial Likert surveys to identify variables that may suggest future drop-out. The completion of ABPM at baseline, 3 months, and 6 months will be recorded, including days to return ABPM device. [name] will mentor [name] in analyzing the barriers in a hypertension trial.

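### The plan promises intention to treat but removes participants from the trial, not only from losartan, after certain adverse events, and nothing keeps them in outcome follow-up

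*Combined protocol and SAP*

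**What the plan says.** Section 2.2 sets the analysis principle: "The study will be analyzed using intention to treat for outcomes which will begin immediately after randomization to losartan". The two arms differ in the clinic BP percentile to be maintained (below the 95th or below the 75th).

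The Data Safety and Monitoring Board paragraph sets the removal rule: "Patients will be withdrawn from the trial if they experience angioedema, recurrent symptomatic hypotension despite dose reduction", followed by "hyperkalemia, or recurrent symptomatic hypoglycemia". Section 7 words other safety actions differently. For liver tests: "If AST/ALT is greater than three times the upper limit of normal, losartan will be stopped". For potassium: "Potassium > 6 mEq/L will be repeated and if abnormal, the dose of losartan will be decreased".

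Section 2.3.b and its table schedule ABPM, urine and blood biomarkers at entry, 3 months and 6 months only, with no early-exit visit. Section 8.3 deals with missed appointments only.

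Section 9.1 wants the change in dipping %, the between-arm difference in nocturnal BP improvement, the within-group SD and the drop-out rate. Section 9.2 compares the arms at the end of the trial with Student's t-test and asks for "the estimated difference in nocturnal blood pressure at baseline and exit". For Objective 4 it adds: "The retention rate will be recorded and re-evaluated against the initial Likert surveys to identify variables that may suggest future drop-out".

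**The concern.** Intention to treat needs outcomes from everyone randomized, including those who stop the drug. The removal rule ends participation for events that occur on treatment, and no text asks for further measurement. Someone removed before month 3 would have no ABPM after baseline and could enter neither the baseline-to-exit difference nor the t-test.

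This matters because the trial exists to supply planning inputs for a definitive trial: a difference, an SD and a drop-out rate. An ABPM that was never taken cannot be recovered at analysis.

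Retention is also affected. It is a secondary objective (section 1.1.b), and section 9.2 relates it to attitude-survey answers. Nothing separates a participant whom the protocol removed from one who chose to leave, although only the second is plausibly explained by attitudes to joining a trial.

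**Working it through.** **The plan's own figures.** 200 × 0.30 = 60 eligible, of whom 40 enroll. At 10% drop-out 40 × 0.90 = 36 remain, which exceeds 30. Drop-out strictly below 10% means at most 3 of 40 lost. More than 30 remain with up to 9 losses (31/40, or 22.5%). These figures agree with each other. No alpha, power, SD or effect size is stated, so there is no power figure to reproduce.

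**Assumptions for an illustration, none from the documents.** 20 per arm (1:1 is implied, not stated); 3/20 withdrawn in the intensive arm and 1/20 in the standard arm; a normal outcome with SD 1; those withdrawn have the highest susceptibility, which has correlation ρ with improvement in the outcome; a true arm difference of 0.50 SD.

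**Shift in a completer mean.** With fraction p removed and c = Φ⁻¹(1 − p), let λ = φ(c)/(1 − p). The shift is −ρλ and the remaining variance is 1 − ρ²(cλ + λ²).

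- p = 0.15: c = 1.036, λ = 0.274. At ρ = 1 the variance is 1 − 0.284 − 0.075 = 0.640 (SD 0.800).
- p = 0.05: c = 1.645, λ = 0.109. At ρ = 1 the variance is 1 − 0.179 − 0.012 = 0.810 (SD 0.900).

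**Arm difference.** The shrinkage is ρ × (0.274 − 0.109), using unrounded values:

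| ρ | Shrinkage (SD) | Observed difference | In 100,000 simulated trials |
|---|---|---|---|
| 0 | 0 | 0.50 | 0.50 |
| 0.5 | 0.083 | 0.417 | 0.42 |
| 1 | 0.166 | 0.334 | 0.34 |

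**Other patterns (simulated).** With equal withdrawals, 2 and 2, the difference stays at 0.50 for every ρ, while the pooled SD falls to 0.96 (ρ = 0.5) or 0.85 (ρ = 1). With all 3 losses that the plan allows falling in one arm (3 versus 0), the difference is 0.50, 0.37 or 0.24 at ρ = 0, 0.5 or 1.

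**Pooled variance, 3 versus 1, ρ = 1.** A two-arm t-test uses (16 × 0.640 + 18 × 0.810)/34 = 0.730, about 27% too low. At ρ = 0.5 the arm variances are 1 − 0.25 × 0.36 = 0.910 and 1 − 0.25 × 0.19 = 0.9525, which pool to 0.9325, about 7% too low.

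**Sample size of a later trial** (assumed two-sided 5%, 80% power). N per arm = 2 × (1.960 + 0.842)² × variance/difference² = 15.70 × variance/difference².

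- Truth: 15.70/0.50² = 62.8, so 63.
- Target difference fixed from outside at 0.50, variance from this trial, ρ = 1: 15.70 × 0.730/0.25 = 45.8, so 46 (too low).
- Both inputs from this trial, ρ = 1: 15.70 × 0.730/0.334² = 102.7, so 103 (too high).
- Both inputs from this trial, ρ = 0.5: 15.70 × 0.9325/0.417² = 84.2, so 85 (too high).

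The error in N therefore has no fixed sign.

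**The case against.** The text does not state that data collection ends at withdrawal; it is silent. Exit is not defined as month 6, so someone removed after month 3 may still contribute the 3-month ABPM. That is fair, but section 7 speaks of stopping losartan where it means the drug, so removal from the trial most naturally means more than that. Silence would also leave staff to decide case by case.

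A reader might infer that the rule loses precisely the strongest responders. The documents do not support this. Of the four triggers only recurrent symptomatic hypotension directly marks a large BP fall. The outcome under evaluation is also dipping %, (awake − sleep)/awake by section 4.3. If awake BP falls proportionally more than sleep BP, dipping % worsens, so losing such participants could overstate improvement. Section 9 does also seek nocturnal BP itself, so this limits the inference without removing the problem.

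A reader might also infer more removals in the intensive arm. The lower target makes that plausible, but no event rates are given. Both arms start at 25 mg, are increased only at monthly visits, and share one cap (sections 6.1 and 6.3). An early removal caused by the arm's target is therefore unlikely.

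Two numerical inferences also fail. Reading the intensive arm's upper-bound variance loss (1 − 0.640 = 36%) as an equal shortfall in planned N ignores pooling and the shrunken difference. Saying that the expected drop-out below 10% is already broken rests on assuming four removals (4/40 = 10%). The plan's stated purpose of more than 30 participants would still be met with 36.

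On retention, AEs are recorded at each visit, so safety removals could be identified afterwards. That stands, but no section says they will be separated in the retention rate.

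**Conclusion.** The conflict is in the text: an intention-to-treat commitment, a rule that ends participation for on-treatment events, and no follow-up or missing-data provision to join them. Followed as written, the end-of-trial comparison is one of completers.

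The size and direction of the bias are not known. The mean difference is biased only if withdrawal both differs by arm and is related to the outcome. Under the assumed 3/20 versus 1/20, the shrinkage runs from 0 through about 0.08 SD (ρ = 0.5) to at most about 0.17 SD (ρ = 1), with the pooled variance about 27% too low in that last case. If all three losses fell in one arm, the simulated shrinkage could reach 0.50 − 0.24 = 0.26 SD. Planned N may come out too low or too high, and the sign for dipping % is open.

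The mixing of mandated removals with voluntary drop-out needs no assumption about correlation or arm imbalance, only that some removals occur. The point should be fixed before follow-up data are lost, but the documents do not show that it invalidates a feasibility trial.

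**What to change.** Add one paragraph to the protocol, with matching consent wording:

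- A participant who stops losartan for any reason remains in follow-up, with the scheduled 3- and 6-month ABPM, urine and blood assessments, unless consent is withdrawn.
- All randomized participants are analysed in their assigned arm, and section 9.2 names a method for ABPMs that are still missing, with a sensitivity analysis.
- Treatment discontinuation is reported by cause and arm, separately from loss to follow-up. Only loss to follow-up counts as the retention rate related to the surveys.

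This leaves unchanged which events stop or reduce losartan. Separately, section 7 (dose decrease for confirmed high potassium) and the Data Safety and Monitoring Board paragraph (withdrawal for hyperkalemia) disagree on who stays in the trial. The sponsor must reconcile them; no clinical rule is proposed here.

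The cost is a short amendment and up to two already scheduled ABPMs in each of a few participants who are off drug. The intention-to-treat estimate will include off-treatment values; an on-treatment summary can be shown beside it.

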## 2.2.c. Exclusion Criteria for Feasibility Trial Screening

1. Participant with history of angioedema to prior ARB or ACE inhibitor
2. Participants with moderate to severe renal impairment (GFR <60mL/min/1.73m^2)
3. Co-administration of another hypertensive medication
4. History of known bilateral renal artery stenosis, unilateral renal artery stenosis to a solitary kidney
5. Hyperkalemia at time of screening (K>6 mmol/L- non-hemolyzed sample)
6. Pregnancy
7. Current use of lithium, digitalis, warfarin

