#### 2.3.b Follow-up

1. Monthly evaluations (6 months total from randomization)
  - a. Participants will have monthly clinic visits
  - b. Obtain vital signs
  - c. Obtain standard of care labs: including CBC, CMP
  - d. Complete assessment of potential side effects of losartan
  - e. Complete assessment of adherence
2. Three months from randomization
  - a. Obtain overnight urine specimens for urine biomarkers including standard evaluation of microalbumin/creatinine ratio and experimental evaluation of biomarkers
  - b. Obtain cystatin C
  - c. Buccal Cell Collection
  - d. Repeat 24 hour ABPM
3. Six months from randomization
  - a. Obtain overnight urine specimens for urine biomarkers including standard evaluation of microalbumin/creatinine ratio and experimental evaluation of biomarkers
  - b. Obtain cystatin C
  - c. Buccal Cell collection
  - d. Repeat 24 hour ABPM

Table XX: Baseline and monthly evaluations

Test	Entry	1 mo	2 mo	3 mo	4 mo	5 mo	6 mo
Vital Signs, Hx and PE	X	X	X	X	X	X	X
CBC with diff	X	X	X	X	X	X	X
CMP	X	X	X	X	X	X	X
Adherence Measures		X	X	X	X	X	X
Ferritin	X			X			X
Cystatin C	X			X			X
Uric Acid	X			X			X
Urine Microalbumin/Creatinine	X			X			X
Overnight Urine Collection	X			X			X
24 hr ABPM	X			X			X
Urine and blood biomarkers	X			X			X
Pregnancy Test	X	X	X	X	X	X	X
Enrollment Survey	X						
Buccal Cell collection	X			X			X

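### Section 7 manages a repeated potassium above 6 mEq/L by reducing the losartan dose, while the DSMB section withdraws patients for unqualified hyperkalemia, and nothing says which rule prevails

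*Combined protocol and SAP*

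**What the plan says.** Section 7 (Safety Reporting and Adverse Events) gives the operating rule: "Participants will have potassium monitored monthly", and "Potassium > 6 mEq/L will be repeated and if abnormal, the dose of losartan will be decreased". If blood pressure is still above the 95th "percentile blood pressure when hyperkalemia, a diuretic will be added as standard of care". That paragraph does not mention withdrawal. For liver enzymes above three times the upper limit, the same section tells staff to stop losartan and says nothing about leaving the trial.

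The Data Safety and Monitoring Board section ends with a different instruction: "Patients will be withdrawn from the trial if they experience angioedema, recurrent symptomatic hypotension despite dose reduction, hyperkalemia, or recurrent symptomatic hypoglycemia".

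The only other level given for hyperkalemia is the screening exclusion in Section 2.2.c: "Hyperkalemia at time of screening (K>6 mmol/L- non-hemolyzed sample". For potassium, mmol/L and mEq/L are the same number.

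Section 2.3.b schedules "Monthly evaluations (6 months total from randomization", with a metabolic profile at each visit and ambulatory monitoring (ABPM) at months 3 and 6. Section 2.2 states: "The study will be analyzed using intention to treat for outcomes which will begin immediately after randomization to losartan". Under Objective 4, Section 9.2 makes retention a planned output, and also ABPM completion: "The completion of ABPM at baseline, 3 months, and 6 months will be recorded, including days to return ABPM device".

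**The concern.** Both rules are mandatory in form, and they point in different directions. A dose reduction presupposes that the participant stays on losartan. Withdrawal ends participation. Two staff members, each following the protocol, could treat the same laboratory result in the same adolescent in opposite ways.

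The second matter is less certain. The DSMB section removes patients from the trial and not merely from the drug, and the available text describes no assessments after withdrawal. Month-3 and month-6 ABPM and laboratory data may then be missing for these participants. If such removals were also counted as dropouts, they would enter the retention rate that Section 9.2 sets against the enrollment survey to look for predictors of drop-out. A removal that the protocol requires says nothing about willingness to stay.

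**Working it through.** **Step 1: the two rules side by side.**

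| | Section 7 | DSMB section |
|---|---|---|
| Level | above 6 mEq/L | none given |
| Repeat test | yes | not mentioned |
| Non-hemolyzed sample | not mentioned (Section 2.2.c only, at screening) | not mentioned |
| Recurrence or failed reduction | not mentioned | attached to hypotension; recurrence also to hypoglycemia; neither to hyperkalemia |
| Action | lower dose; diuretic if BP still high | withdraw from the trial |

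The sentence in the DSMB section adds qualifiers to two of its four triggers and leaves hyperkalemia bare, as it does angioedema. No higher potassium level appears anywhere in the available text.

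**Step 2: Section 7 does not cover every case.** All participants start at 25 mg (Section 6.1), and doses are rounded to 25 mg tablets (Section 6.3). No lower step is described for a participant still at 25 mg.

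**Step 3: the plan's own figures (Section 9.1).** Eligible: 200 × 0.30 = 60. Enrolled: 40, so 40/60 = 66.7% acceptance. At 10% dropout, 40 × 0.90 = 36 remain, which exceeds 30. These figures reproduce.

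**Step 4: occasions.** With full retention, months 1 to 6 give 40 × 6 = 240 potassium results. A month-6 result cannot cost a later scheduled visit, so 40 × 5 = 200 are relevant to loss of follow-up.

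**Step 5: effect per case, if withdrawal ends assessments.** Follow-up ABPMs planned: 40 × 2 = 80.

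| Withdrawn at month | ABPMs lost | Share of 80 |
|---|---|---|
| 1 or 2 | 2 | 2.5 points |
| 3 | 2 if that month's ABPM is not yet done, otherwise 1 | 2.5 or 1.25 points |
| 4 or 5 | 1 | 1.25 points |
| 6 | 1 if that month's ABPM is not yet done, otherwise 0 | 1.25 or 0 points |

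If counted as a dropout, one case adds 1/40 = 2.5 points overall, or 1/20 = 5 points in an arm of about 20. The expectation of under 10% corresponds to at most 3 dropouts (3/40 = 7.5%; 4/40 = 10%). The target of more than 30 participants tolerates 40 − 31 = 9 losses.

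**Step 6: range over assumed rates.** The documents give no hyperkalemia rate. The rates below are assumptions: the share of participants withdrawn for it over six months, taken as independent. P(at least one) = 1 − (1 − r)^40. Remaining = 40 × (0.90 − r), which adds these losses to a full 10% dropout.

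| Assumed r | Expected cases of 40 | P(at least one) | Remaining |
|---|---|---|---|
| 1% | 0.4 | 33% | 35.6 |
| 2.5% | 1 | 64% | 35 |
| 5% | 2 | 87% | 34 |
| 10% | 4 | 98.5% | 32 |
| 15% | 6 | 99.8% | 30 |

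In this range the target of more than 30 is missed only at 15% on top of a full 10% dropout.

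**The case against.** The best defense is a stepwise reading. Section 7 is the working procedure, the DSMB sentence is a summary in a section on oversight, and withdrawal is meant only when dose reduction fails, as that sentence says for hypotension. This is plausible and may be the intent. It also answers the complaint that the DSMB sentence has no repeat test, since Section 7 supplies one. It is not written for potassium, however, so the ambiguity stands.

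Several stronger inferences are tempting and should not be drawn:

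- **That the DSMB section orders withdrawal at a confirmed level above 6.** It states no level and no confirmation. The conflict arises because nothing limits the term, not because a second threshold is given.
- **That follow-up certainly stops.** No text says so. It is inferred from the withdrawal wording and the absence of any post-withdrawal schedule.
- **That this contradicts intention to treat.** Withdrawal may create missing outcomes, but analysis by randomized arm remains possible.
- **That retention must fall.** The plan does not say whether a required removal counts as a dropout, and reasons could be separated in the review under Objective 4.
- **That those removed had drug-related events.** The DSMB section does not require attribution to losartan.
- **That each case uses up a fixed dropout allowance.** The figure of under 10% is an expectation in support of more than 30 participants.

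Keeping participants in assessment after losartan stops is also partly a design choice. Usual care is an antihypertensive (Potential Risks), so later readings may reflect another drug, in a trial meant to inform losartan's effect size and variability. That stands, and the fix allows for it.

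**Conclusion.** The two sections leave one safety instruction unreconciled, and this should be fixed. Confidence is high, because it rests on the wording alone: mandatory dose reduction in one place, mandatory withdrawal without qualification in the other, and no order of precedence in the available text.

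The loss of month-3 and month-6 data is secondary and conditional. It assumes that withdrawal from the trial ends assessments and that no provision elsewhere keeps them. On that assumption, one case costs none to two follow-up ABPMs, depending on timing. The trial-level effect cannot be estimated without a hyperkalemia rate and is probably small. Section 9.1 says the trial is meant to inform a definitive study and not to test efficacy, so the stake is a clear safety rule and clean feasibility data. No trial decision is under threat.

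**What to change.** Write one potassium rule and use it in both sections. For example: repeat any value above 6 mEq/L on a non-hemolyzed sample, reduce losartan if confirmed, and stop losartan if it recurs or persists despite reduction. The rule should also say what to do at 25 mg. The clinical choice is the sponsor's.

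In the DSMB section, replace trial withdrawal with discontinuation of losartan, and add that the scheduled 3- and 6-month assessments continue for participants who consent. Report drug discontinuations separately from study dropouts. Report on-drug blood pressure estimates alongside the intention-to-treat results, since off-losartan readings may reflect another antihypertensive.

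The cost is amendment wording, plus keeping at most two already scheduled ABPMs and the related laboratory tests per affected participant. At $25 per ABPM (Section 11), family payments come to at most 2 × $25 = $50.
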